6.6 Study Beginning and End/Completion

6.6.1 Definition of Beginning of the Study

The beginning of the study will be defined as the beginning of the screening (ie, signing of the ICF) of the first participant.

6.6.2 Definition of End of the Study

The end of study is defined as the date of the last scheduled study procedure as outlined in the Schedule of Study Procedures (Section 3.0).

6.6.3 Definition of Study Completion

The end of the study is scheduled after completion of the evaluations in the follow-up visit for the last participant in the study.

This time period may change in the event that the study is terminated early or the last participant is lost to follow-up.

6.6.4 Definition of Study Discontinuation

The clinical site(s) reserve(s) the right to terminate the study in the interest of participant welfare.

The Sponsor reserves the right to suspend or terminate the study at any time.

6.6.5 Criteria for Premature Termination or Suspension of the Study

The study will be completed as planned unless one or more of the following criteria are satisfied that require temporary suspension or early termination of the study:

- New information or other evaluation regarding the safety or efficacy of the study medication that indicates a change in the known risk/benefit profile for the product, such that the risk is no longer acceptable for participants participating in the study.

- Significant violation of Good Clinical Practice (GCP) that compromises the ability to achieve the primary study objectives or compromises participant safety.

6.6.6 Criteria for Premature Termination or Suspension of a Site

6.6.6.1 Criteria for Premature Termination or Suspension

A study site may be terminated prematurely or suspended if the site (including the Investigator) is found in significant violation of GCP, the study protocol, or contractual agreement; if the site (including the Investigator) is unable to ensure adequate performance of the study; or as otherwise permitted by the contractual agreement.

6.6.6.2 Procedures for Premature Termination or Suspension

In the event that the sponsor, an Institutional Review Board (IRB)/Independent Ethics Committee (IEC), or a regulatory authority elects to terminate or suspend the participation of an investigational site, a study-specific procedure for early termination or suspension will be provided by the sponsor; the procedure will be followed by applicable investigational site(s) during the course of termination or study suspension.

7.0 SELECTION AND DISCONTINUATION/WITHDRAWAL OF PARTICIPANTS

7.1 Inclusion Criteria

7.1.1 Inclusion for Participants with Hepatic Impairment

Participants must fulfill the following inclusion criteria to be eligible for participation in the study (participants who do not qualify based on a reversible condition or mild intercurrent illness may be re-screened after the condition is resolved. Screening tests may be repeated if in the Investigator's opinion the test needs to be repeated):

1. Is an adult male or female participant aged ≥ 18 to < 75 years, at screening.
2. Has a BMI ≥ 18.0 and $\leq 40.0 \text{ kg/m}^2$, at screening. At least 50% of the participants will be required to be of BMI ≥ 18.0 and $\leq 35.0 \text{ kg/m}^2$, at screening.
3. Aside from HI, be sufficiently healthy for study participation based upon medical history, physical examination, vital signs, ECGs, and screening clinical laboratory profiles, as deemed by the Investigator or designee.
 - Supine BP is $\geq 80/40 \text{ mmHg}$ (asymptomatic) and $\leq 150/95 \text{ mmHg}$, at screening;
 - Supine PR is $\geq 40 \text{ bpm}$ and $\leq 99 \text{ bpm}$, at screening;
 - QTcF is $\leq 500 \text{ msec}$ and ECG findings considered normal or not clinically significant by the Investigator or designee, at screening.
4. The participant must have had chronic HI for at least 3 months before screening, and the HI must be stable, ie, no significant changes in hepatic function in the 30 days preceding

screening (or since the last visit if within 6 months before screening) and treatment with stable doses of medication. Has a score on the Child-Pugh Class at screening as follows:

- (Arm 1) Moderate HI, Child-Pugh Class B: ≥ 7 and ≤ 9
- (Arm 2) Mild HI, Child-Pugh Class A: ≥ 5 and ≤ 6

5. Participants should not have renal dysfunction as demonstrated by a relatively adequate renal function (creatinine clearance ≥ 50 mL/min), at screening.

7.1.2 Inclusion for Healthy Participants

Participants must fulfill the following inclusion criteria to be eligible for participation in the study:

1. Is an adult male or female participant aged ≥ 18 to < 75 years, at screening. Healthy participants will be matched to hepatic impaired participants in this study by sex (± 2 per sex) and by age (mean ± 10 years).
2. Has a BMI ≥ 18.0 and ≤ 40.0 kg/m², at screening. At least 50% of the participants will be required to be of BMI ≥ 18.0 and ≤ 35.0 kg/m², at screening. Healthy participants will be matched to hepatic impaired participants in this study by BMI (mean $\pm 10\%$).
3. Medically healthy with no clinically significant medical history, physical examination, laboratory profiles, vital signs or ECGs, as deemed by the Investigator or designee.
 - Supine BP is $\geq 90/40$ mmHg and $\leq 150/95$ mmHg, at screening;
 - Supine PR is ≥ 40 bpm and ≤ 99 bpm, at screening;
 - QTcF is ≤ 450 msec (males) or ≤ 470 msec (females) and ECG findings considered normal or not clinically significant by the Investigator or designee, at screening;
 - Liver function tests including ALT, AST, ALP and total bilirubin \leq the ULN at screening and check-in.
4. Participants should not have renal dysfunction as demonstrated by a relatively adequate renal function (creatinine clearance ≥ 60 mL/min), at screening.

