4.2 Rationale for the Proposed Study

In this study, the impact of HI on the PK of single dose soticlestat [REDACTED]. After entering the body, drugs are eliminated by excretion and/or metabolism. Although elimination can occur through a variety of routes, most drugs are cleared by metabolism in the liver and/or small intestine and/or by elimination of unchanged drug by the kidney. Liver disease is associated with several pathophysiologic changes that may alter the PK of a drug. These include alterations in hepatic blood flow, changes in liver enzyme activity, decreased binding of drug to plasma proteins, and impaired biliary excretion [2, 3]. Accordingly, current United States (US) FDA guidance recommends a PK study in patients with impaired hepatic function if hepatic metabolism and/or excretion accounts for a substantial portion ($\geq 20\%$ of the absorbed drug) of the elimination of a parent drug or active metabolite [4].

The magnitude of the effect of mild, moderate, or severe HI on the PK of soticlestat was assessed based on model-based simulations of HI effect using in vitro enzyme phenotyping data and data from the human ADME study. The simulations suggested that in participants with mild, moderate, or severe HI, soticlestat AUC_{∞} is expected to be 1%, 23%, and 33% higher, respectively, than healthy participants with normal hepatic function; soticlestat C_{max} is expected to be 0%, 6%, and 7% higher, respectively, compared with healthy participants with normal hepatic function.

Based on model-based simulations, this study first evaluated the PK in participants with moderate HI (n=8) and healthy matched participants with normal hepatic function (n=12) and an interim PK analysis was conducted. The interim analysis indicated higher impact of moderate HI on soticlestat PK than the model predicted. For participants with moderate HI, soticlestat PK exposure increased to 214.93%, 316.47%, and 299.38% for C_{max} , AUC_{last} , and AUC_{∞} , respectively, when compared to the respective PK exposure in matched participants with normal hepatic function. As a result, this study will further evaluate the impact of mild HI on the PK of soticlestat. In addition, the Sponsor decides not to dose participants with severe HI. Soticlestat will not be recommended to use in subjects with severe HI.

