6.0 STUDY DESIGN AND DESCRIPTION

6.1 Study Design

This is a phase 1, open-label, study of oral soticlestat designed to assess the PK of single dose soticlestat [REDACTED] in participants with moderate or mild HI compared to matched healthy participants with normal hepatic function. At least 12 healthy participants (up to 24 participants) with normal hepatic function will be recruited to match the group mean of moderate and mild HI arms by age (mean \pm 10 years), sex (\pm 2 per sex), and BMI (mean \pm 10%). Eight (8) participants will also be enrolled in each HI arm of the study according to the following criteria:

- Arm 1: (N = 8): Moderate HI (Child-Pugh Class B [Score: ≥ 7 and ≤ 9]), 300 mg single dose
- Arm 2: (N = 8): Mild HI (Child-Pugh Class A [Score: ≥ 5 and ≤ 6]), 300 mg single dose
- Arm 3: (N = 12 - 24): Normal hepatic function, 300 mg single dose

The study will consist of a 28-day screening period (prior to dosing) and a 7-day confinement period (Day -1 to Day 7).

Two hepatic function assessments are required prior to Day 1 dosing for participants with HI. These 2 assessments should be obtained during the screening period and at least 48 hours apart. In the case, where a participant has an available historical Child-Pugh assessment score within 3 months prior to screening, 1 assessment can be conducted during the screening period. If the Child-Pugh scores from these 2 assessments indicate the same liver function category for the participant (ie, normal hepatic function, moderate HI, or mild HI), soticlestat can be administered as scheduled. If the results of the 2 assessments indicate different liver function categories, a third assessment must be conducted at least 24 hours after the second assessment. If the results of the 2 most recent assessments (the second and third) are in agreement with regard to the participant's liver function category, the participant may be enrolled and should receive the Day 1 dose within 48 hours of the third assessment. If the second and third measurements differ, the participant will not be eligible for the study.

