The moderate HI arm (ie, Arm 1) will be conducted first, followed by 12 participants in the matched normal hepatic function arm (Arm 3). After all participants in moderate HI arm and the matching 12 participants in the matched normal hepatic function arm have completed the treatment period, an informal interim PK data analysis is planned and may additionally leverage historical control PK data in healthy participants to gain an initial estimate of the effect of moderate HI on the PK of soticlestat [REDACTED].

Following completion of enrolment of the mild HI arm, and in the instance any of the previously enrolled healthy participants cannot be used for matching purposes, up to an additional 12 participants may be enrolled for the matched normal hepatic function group (Arm 3) to ensure a minimum of 12 participants with normal hepatic function and matching the mean of the mild HI arm by age (mean \pm 10 years), sex (\pm 2 per sex), and body mass index (BMI, mean \pm 10%) are enrolled.

Participants will receive a single oral dose of 300 mg soticlestat as three 100 mg T4 tablets on Day 1 with approximately 240 mL water under fasting conditions. PK samples will be collected from Days 1 to 7, at predetermined time points (Section 3.0), to characterize the PK of soticlestat [REDACTED] in participants with moderate or mild HI compared to matched healthy participants with normal hepatic function (Section 3.0).

Participants will remain in the clinic throughout the study. Participants will be discharged from the clinic on Day 7 after the last PK sample collection and study procedures are completed. A safety follow-up contact of all participants (including those who terminate the study early) will occur 14 \pm 2 days after the soticlestat dose to determine if any AEs have occurred since the CRU discharge.

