This study will investigate the impact of impaired hepatic function on the plasma PK of soticlestat [REDACTED] and safety compared to matched healthy participants with normal hepatic function in order to provide dosing recommendations to clinicians for future treatments of soticlestat to patients with varying degrees of HI. An informal interim PK data analysis was performed following soticlestat administration in participants with moderate HI ($n=8$) and healthy matched participants with normal hepatic function, which has demonstrated higher than expected soticlestat exposure in participants with moderated HI than in healthy matched participants with normal hepatic function. The Sponsor has decided not to recommend soticlestat dosing in patients with severe HI, therefore participants with severe HI will not be enrolled in the current study. Instead, this study will enroll an arm of participants with mild HI in order to further investigate the impact of HI on soticlestat PK. Due to the variability of soticlestat PK and easier accessibility of healthy participants in comparison to participants with HI, an increased number of healthy participants will be enrolled.

The Child-Pugh classification will be used to categorize HI due to its widespread use and acceptance by regulatory agencies (including the FDA). It has been shown to correlate with hepatic (ie, metabolic) clearance for several compounds [4]. In the current study, participants with chronic, stable HI with features of cirrhosis due to any etiology will be enrolled using the

Child-Pugh scale. The scale employs five clinical measures of liver disease listed in [Table 6.a](#). Each assessment is scored 1 - 3, with 3 indicating most severe derangement. Participants' scores of 5 to 6, 7 to 9, and 10 to 15 on this scale are classified as having mild, moderate, and severe HI, respectively.

Table 6.a Derivation of Child-Pugh Classification Score¹

Parameter	1 point	2 points	3 points
Serum albumin (g/dL)	>3.5	2.8 to 3.5	<2.8
Total serum bilirubin (mg/dL)	<2.0	2.0 to 3.0	>3.0
Prothrombin time (PT) (second prolonged) or International normalized ratio (INR) (ratio)	<4 <1.70	4 to 6 1.70 to 2.30	>6 >2.30
Ascites	Absent	Slight	Moderate or participants on medication to control ascites
Hepatic encephalopathy grade	None	Grade 1 or 2	Grade 3 or 4 or participant receiving medication(s) to prevent encephalopathy

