8.1.3 Clinical Study Drug Blinding

This is an open-label study.

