Individual plasma soticlestat (total and unbound), [REDACTED] AUC_{∞} values for participants with moderate and mild hepatic impairment as well as healthy participants will be plotted versus serum alpha-1-acid glycoprotein, serum albumin, total serum bilirubin, and INR ratio. In addition, individual plasma soticlestat (total and unbound), [REDACTED] AUC_{∞} values will be plotted versus Child-Pugh scores in participants with moderate and mild hepatic impairment.

[figure not shown]
Analysis of Variance (ANOVA)

An ANOVA will be performed on the ln-transformed C_{max} , AUC_{last} , and AUC_{∞} for total soticlestat, [REDACTED] to compare each HI group (moderate HI and mild HI) with the normal matched hepatic function group, where 90% CIs for the ratio of GMRs from each HI group versus normal matched function group will be provided. For total [REDACTED] an ANOVA will also be performed on the ln-transformed PK parameters for MRC_{max} , $MRAUC_{last}$, and $MRAUC_{\infty}$. The addition of other factors and covariates such as age, sex, and BMI on the relationship between soticlestat PK parameters and level of HI may also be investigated.

The ANOVA model will include hepatic function (Moderate HI, Mild HI, Normal Matched Hepatic Function) group as a fixed effect. GMRs and 90% CIs will be calculated from the exponentiated difference between group least squares means and corresponding 90% CIs from the analyses on the ln-transformed C_{max} , AUC_{last} , AUC_{∞} , MRC_{max} , $MRAUC_{last}$, and $MRAUC_{\infty}$. The GMRs and 90% CIs will be expressed as a percentage relative to the Normal Hepatic Function group.

The above statistical analyses will also be performed on the ln-transformed $C_{max,u}$, $AUC_{last,u}$, and $AUC_{\infty,u}$ for unbound soticlestat.

If all subjects in the healthy group are matched to both the moderate HI and mild HI groups, the ANOVA analysis will be performed using the following SAS® code. Note that due to expected differences in the variability of PK parameter values between groups, the residual variance will be estimated separately for each group with use of the repeated statement, and variance components as the covariance matrix structure:

[figure not shown]

Where 'Arm' is as described in [Section 2.0](#) where 1=Moderate HI, 2=Mild HI, 3=Normal Function. Appropriate coefficients will be used based on the input variable for arm.

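### Does the unscaled sex tolerance leave the healthy comparator for mild hepatic impairment open to choice?

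*Protocol*

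**What the plan says.** The matching rule appears in several places. Protocol 7.1.2 reads "Healthy participants will be matched to hepatic impaired participants in this study by sex (± 2 per sex", next to tolerances of 10 years around the mean for age and 10% around the mean for BMI. The general design paragraph of Protocol 6.1 says healthy participants "will be recruited to match the group mean of moderate and mild HI arms by age" and by sex and BMI. A later paragraph of 6.1, repeated in Protocol 1.0, Protocol 6.5 and SAP 2.0, deals with the mild comparison. It requires at least 12 healthy participants matched to the mild arm on the same three criteria, and permits up to 12 more "in the instance any of the previously enrolled healthy participants cannot be used for matching purposes".

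SAP 6.8 has two routes. One three-group ANOVA is used "If all subjects in the healthy group are matched to both the moderate HI and mild HI groups". Otherwise each HI arm is analysed with its own matched healthy group in a separate subset. Both documents describe a descriptive study with no hypothesis, no decision rule and no power calculation.

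On timing, Protocol 4.2 records that "this study first evaluated the PK in participants with moderate HI (n=8) and healthy matched participants with normal hepatic function (n=12") and that the interim PK analysis of these participants has been done.

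**The concern.** Age and BMI tolerances are tied to a mean; the sex tolerance is a bare number applied to groups of 8 and of 12 to 24. Matching is defined on group totals and means, so no single control passes or fails, yet the protocol speaks of individual controls who cannot be used. Neither document says who belongs to the mild-matched set, who decides, or when.

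The timing sharpens this. Protocol 8.1.3 states "This is an open-label study", the controls' concentrations have been analysed, and any top-up follows completion of mild-arm enrolment. The mild-HI ratios for C_max, AUC_last and AUC_∞ are the primary result still to come, and the study is run "in order to provide dosing recommendations to clinicians for future treatments of soticlestat to patients with varying degrees of HI". If membership could be settled with control values in view, the denominator of that result would not be fixed in advance.

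**Working it through.** **1. Planned size.** 8 moderate + 8 mild + up to 24 healthy = 40, which reproduces the maximum in Protocol 1.0. No between-subject CV is given, so CVs below are assumed.

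**2. Reference group.** Protocol 7.1.2 refers to the hepatic impaired participants, the opening of 6.1 to both HI arms, and the later paragraph of 6.1 (with 1.0, 6.5 and SAP 2.0) to the mild arm. The first two are general descriptions. The last is the specific rule for the mild comparison, so that reference is stated.

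**3. Unit of the tolerance.** Let an HI arm have m men of 8, and the control group x men of n.

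- Raw count: |x − m| ≤ 2 and |(n − x) − (8 − m)| ≤ 2. Together these give n − 8 ≤ 4. At n = 12 only x = m + 2 passes; above 12 nothing passes.
- Scaled: |x − m·n/8| ≤ 2. At n = 12, m = 4 allows 4 to 8 men and m = 6 allows 7 to 11. At n = 24, m = 4 allows 10 to 14 and m = 6 allows 16 to 20.

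Only the scaled reading fits a combined Arm 3 anywhere in its planned range of 12 to 24. A raw count could survive only by keeping separate sets of exactly 12.

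**4. How often the readings disagree on reusing all 12.** Suppose the first 12 controls were recruited by raw count to a moderate arm with m1 men, giving m1 + 2 men. For a mild arm with m2 men, the raw count permits full reuse only if m2 = m1. The scaled rule permits it if |m1 + 2 − 1.5·m2| ≤ 2, which holds for three values of m2 at each m1, one of them m2 = m1. That gives 2 × 9 = 18 disagreements in 81 pairs. With both arms Binomial(8, p), the probability is 0.416, 0.422, 0.413, 0.393 and 0.367 at p = 0.5, 0.6, 0.7, 0.75 and 0.8.

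The calculation assumes the raw count was already applied to the moderate arm. If it was, practice has settled the rule. If it was not, the control composition is different and these figures do not apply.

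**5. How often a control must leave because of sex.** Same starting composition, scaled rule, up to 12 additions. Example with m1 = 6 (8 men, 4 women):

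| Mild-arm men | Additions needed | Check: men vs target |
|---|---|---|
| 4, 5, 6 | none | 8 vs 6, 7.5, 9 of 12 |
| 3 | 4 women | 8 vs 6 of 16 |
| 7 | 4 men | 12 vs 14 of 16 |
| 2 | 12 women | 8 vs 6 of 24 |
| 0, 1, 8 | cannot be met by adding | a control must leave |

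Over all pairs, the probability that a control must leave is 5.5%, 6.6%, 9.7%, 12.2% and 15.9% at the same five values of p.

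**6. Effect on the ratio if controls leave.** Take SD = √ln(1 + CV²) = 0.294, 0.472, 0.703 at CV 30%, 50%, 80%. Expected top order statistics of 8 normal values are 1.4236 and 0.8522 SD. Let S = 1.4236 (one of 8 men dropped and replaced) or 1.4236 + 0.8522 = 2.2758 (two). Highest-versus-lowest gap = exp(2·S·SD/12); one-way shift against a PK-blind choice = exp(S·SD/12). The 90% CI factor for 8 versus 12 is exp(t(0.95, 18)·SD·√(1/8 + 1/12)).

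| CV | Gap, one / two dropped | One-way shift, one / two | 90% CI factor |
|---|---|---|---|
| 30% | 1.072 / 1.118 | 1.035 / 1.057 | 1.262 |
| 50% | 1.119 / 1.196 | 1.058 / 1.094 | 1.453 |
| 80% | 1.182 / 1.306 | 1.087 / 1.143 | 1.745 |

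A separate simulation allowed any of the 12, not only the men, to leave. With two dropped, the median extreme gap was 1.14 at CV 30% and 1.24 at CV 50%. Two choices made at random differed typically by only 1.03 and 1.05.

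**7. Choice of ANOVA route.** With a separate residual variance per group, the mild-versus-normal contrast and its standard error use only those two groups. For the same controls the two routes in SAP 6.8 agree, provided the subset code (not reproduced in the text) keeps those variances.

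**The case for a change.** The strongest reply is that a confidence interval does not cover selection made with outcomes in view, so comparing the shift with the interval width is not a full answer. The simulated effect of Protocol 4.2, under which mild-HI AUC_∞ "is expected to be 1%, 23%, and 33% higher, respectively, than healthy participants with normal hepatic function" (mild, moderate and severe in that order), is 1%, well below the possible shifts. Stating a rule would also cost only a few sentences.

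The first part stands as a statement about the text: neither document excludes knowledge of the controls' PK when the set is chosen. But the shift needs deliberate selection on PK, which nothing in the documents suggests. The 1% is a weak yardstick, since the same simulation gave 23% for moderate HI and the interim ratio of 299.38% is 199% higher.

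The obvious rules also gain little. Removing the last enrolled of a sex first deals with sex alone, leaves open which controls go if the age or BMI mean fails, and may remove a better match on those. Dating a membership list before mild-arm concentrations are released does not undo knowledge of the controls' values. Meanwhile SAP 6.3 and 6.4.1 already require disposition and demographics separately for the mild-matched, moderate-matched and overall normal groups. Those tables do not prespecify membership, but they show the composition of each set.

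**Conclusion.** The wording is incomplete, but no change to the plan follows. The reference group for the mild comparison is stated, no figure is wrong, and a scaled count is a workable reading at every permitted control group size. Keeping the earlier controls and adding where needed satisfies the sex tolerance in roughly 84% to 95% of cases. This assumes independent recruitment of both arms with male probability 0.5 to 0.8 and first controls at the raw-count composition; age and BMI limits were not modelled.

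If all 12 controls stay and none are added, membership has no effect. If some leave, a choice on age, sex and BMI made without regard to PK has no expected shift relative to a random drop. Gap factors of 1.07 to 1.31 are conditional bounds for dropping one or two of 8 men deliberately, at assumed CVs of 30% to 80%; the one-way shift of 4% to 14% stays below the CI half-width. In a descriptive study without a decision rule, this is a detail that competent analysts can settle soundly. The clinical pharmacology analysis plan was not available, and the SAP's account of its contents does not mention matching.
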